12.3. Eczema Area and Severity Index (EASI)

Investigators will use the EASI to assess each subject's extent and severity of atopic dermatitis at Visit 1 and then at every protocol defined treatment visit.

The EASI divides the subject's body down into four body regions:

- Head and Neck
 - Face occupies 33% (17% each side), neck 33% (17% front and back) and scalp 33% of the head and neck region
- Trunk (including genital areas)
 - Front occupies 55% and back 45% of the trunk
- Upper limbs

- Each arm occupies 50% of the upper limbs region (front or back of one arm is 25%)
- Lower limbs (including buttocks)
 - Each leg occupies 45% (front or back of one leg is 22.5%) and buttocks 10% of the lower limbs region

An area score is recorded for each of the four regions of the body. The area score is the percentage of skin affected by AD for each body region.

Table 6: Area Score

Area Score	Percentage of skin affected by AD in each region
0	No active AD in this region
1	1-9%
2	10-29%
3	30-49%
4	50-69%
5	70-89%
6	90-100%; the entire region is affected by AD

The severity score is recorded for each of the four regions of the body. The severity score is the sum of the intensity scores for four signs. The four signs are:

- Redness (erythema, inflammation)
- Thickness (induration, papulation, swelling-acute AD)
- Scratching (excoriation)
- Lichenification (lined skin, furrowing, prurigo nodules-chronic AD)

The *AVERAGE* intensity of each sign in each body area is assessed according to the following table:

Table 7: Severity Score

Score	Intensity of redness, thickness/swelling, scratching, lichenification
0	None, absent
1	Mild (just perceptible)
2	Moderate (obvious)
3	Severe

Half scores are allowed. In darker skin type subject's, it may be difficult to assess redness and in this case increase the average redness score by 1 level.

Table 8: Four signs of AD used to calculate EASI severity score

Intensity	None	Mild	Moderate	Severe
Redness				
	Score 0	Score 1	Score 2	Score 3
Thickness/induration papulation/oedema				
	Score 0	Score 1	Score 2	Score 3
Scratching				
	Score 0	Score 1	Score 2	Score 3
Lichenification/prurigo				
	Score 0	Score 1	Score 2	Score 3

(Hanifin, 2001)

12.4. Signs of Atopic Dermatitis (SAD)

The Signs of Atopic Dermatitis (SAD) assessment is the investigator's assessment of the average overall severity of signs of AD in each target AD evaluation area at a particular time-point. The investigator should NOT refer to any other assessments to assist with these assessments.

At Visits 2 through 6, the investigator will assess the signs of AD using the scales below and report the one integer that best describes the average overall severity of each of the signs in each target treatment area. Any new areas of AD that develop outside the baseline identified target treatment areas will not be assessed by the SAD.

This assessment must be done at Visit 2 prior to the first study medication application. This assessment must be done at Visits 3-6 either prior to the first study medication application or approximately 4 hours after the most recent study medication application.

ERYTHEMA (REDNESS)	
Grade	Descriptor
0	None: No redness
1	Mild: Barely perceptible, light redness
2	Moderate: Definite redness, easily detectable
3	Severe: Marked, deep/dark red

INDURATION (ELEVATION)	
Grade	Descriptor
0	None: No elevation
1	Mild: Barely perceptible elevation, may be more palpable than visually perceptible; scattered
2	Moderate: Definite visually perceptible elevation; not extensive/moderate coverage
3	Severe: Marked and obvious elevation; extensive presence/significant coverage

LICHENIFICATION (EPIDERMAL THICKENING)	
Grade	Descriptor
0	None: No epidermal thickening
1	Mild: Minimally perceptible epidermal thickening, skin lines may be slightly accentuated
2	Moderate: Definite epidermal thickening, skin lines accentuated/pronounced
3	Severe: Marked epidermal thickening, skin lines and very pronounced

EXCORIATION (SIGNS OF SCRATCHING)	
Grade	Descriptor
0	None: No skin damage
1	Mild: Minimal damage to the top layer of skin, there may be a suggestion of linear pattern to the damage
2	Moderate: Definite damage/loss of the top layer of the skin with perceptible linear pattern
3	Severe: Marked damage/loss of the top layer of the skin, pronounced linear pattern of damage

OOZING/CRUSTING (EXUDATION)	
Grade	Descriptor
0	None: No oozing or crusting

1	Mild: Barely perceptible oozing, lesions may or may not be moist, no crusting
2	Moderate: Definite oozing, lesions damp to the touch, crusting may be present
3	Severe: Marked oozing, lesions are wet, crusting present

12.5. Subjects Pruritis Assessment (SPA)

The SPA is the subject's assessment of the worst severity of pruritus, a symptom of AD, in each of the target evaluation areas of AD during the 24 hours prior to each follow up visit. The subject should NOT refer to any other assessments or any other active areas of AD outside the bilateral target evaluation areas to assist with these assessments.

At Visits 2 through 6, the subject will perform the SPA using the 11-point numeric rating scale below and report the one integer that best describes the worst severity of pruritus on each target evaluation area (identified at baseline) over the previous 24 hours.

PRURITUS (ITCHING)	
Grade	Descriptor
0	No itch
1	
2	
3	
4	
5	
6	
7	
8	
9	
10	Worst possible itch

To complete the SPA, the study coordinator should show the SPA scale to the subject, explain the scale and ask the subject to indicate which integer best describes the worst pruritus the subject experienced on each target evaluation area of AD over the previous 24 hours.

This assessment must be done at Visit 2 prior to the first study medication application. This assessment must be done at Visits 3-6 either prior to the first study medication application or approximately 4 hours after the most recent study medication application.

12.6. AD Treatment Area Photography

Canfield Scientific will supply all investigational sites with study specific camera equipment to photograph each subject's identified target AD treatment areas. Sites will be supplied with color stickers to identify each target area. Details regarding the use of the equipment and how to upload the photographs to the Canfield database will be supplied to the sites in a study specific Canfield study manual.

At Visit 1, investigational sites must identify and photograph the proposed target AD treatment areas that will be treated and followed throughout the duration of the study. These standardized photographs will be submitted to Canfield and reviewed by a panel of 3 dermatologists prior to allowing the subject to be enrolled to the study. The photographs will be assessed by the panel of dermatologists to confirm that the subject meets the protocol defined inclusion in the study. In cases where the photographs do not properly characterize the disease (due to flashback and whitening on the photographs) the subjects will be allowed to enroll to the study based upon the Principal Investigator's clinical assessment of the subject.

Sites will be required to photograph each target AD treatment area at all protocol defined treatment visits.

13. ASSESSMENT OF SAFETY

13.1. Safety Parameters

Safety will be assessed throughout the study by the investigator or a designated and appropriately trained staff member.

13.1.1. Demographic/Medical History

During the screening visit (Visit 1), the investigator or designee will interview each subject to obtain demographic information including date of birth, sex at birth, Fitzpatrick skin type, race and, if appropriate, ethnicity. The investigator or designee will interview each subject to obtain medical history information related to all medical conditions, surgeries and disease states that, at screening: are ongoing, require concomitant therapy or are, in the opinion of the investigator, relevant to the subject's study participation. In addition, the medical history of women who are not of childbearing potential should reflect the reason e.g. post-menopausal for 1 year or greater, total hysterectomy. Information regarding the subject's prior treatments or therapies related to AD must be documented.

13.1.2. Vital Signs

Vital signs will be measured at each visit during the study. The following items will be measured:

- Body temperature
- Heart rate
- Respiration rate
- Blood pressure (systolic and diastolic) after the subject sits quietly for at least 5 minutes
- Height (at Visit 2 only)
- Weight (at Visit 2 only)

Any measure that is, in the opinion of the investigator, abnormal AND clinically significant (CS) must be recorded as history if found prior to the first study medication application, or as an AE if found after the first study medication application begins.

13.1.3. Physical Examination

The investigator or designee will perform a physical examination for all body systems (general appearance, examination of head, eyes, ears, nose and throat, respiratory, cardiovascular, abdominal, neurological, musculoskeletal, lymphatic and skin assessment) at Screening (Visit 1) and end of study (Visit 6).

13.1.4. Electrocardiogram (ECG)

Standard 12-lead ECGs will be performed by a qualified staff member at Screening (Visit 1), Day 8 (Visit 3), Day 15 (Visit 4), Day 29 (Visit 5) and Day 56 (Visit 6/End of Study). The ECGs must be obtained using a standard 12-lead ECG with a 10mm/mV amplitude, at 25mm/sec and a 5 to 10 second duration. To ensure a steady heart rate the subject must rest quietly in the supine position for at least 5 minutes prior to performing the ECG.

A central cardiology laboratory will provide ECG equipment, supplies and site training. In addition, the central cardiology laboratory will process ECGs received by the sites and report results via a secure study portal. The ECG results will be interpreted by a qualified health professional (evaluator) and the interpretation reported either directly on the tracing or in a separate report. The evaluator will interpret the results of every ECG and define the ECG as “normal” or “abnormal”. Variations such as minor ST changes (i.e., <0.5mm depression) and early re-polarization are considered normal.

The investigator must review the evaluator’s interpretation of each subject’s screening ECG prior to Visit 2. The investigator will review the evaluator’s interpretation of all ECG reports in a timely manner and comment on the clinical relevance of any result that is defined by the evaluator as abnormal.

Any abnormalities that are, in the opinion of the investigator, clinically significant, must be reported as history if found prior to the start of the first dose of study medication or as an AE if found after the start of the first dose of study medication

13.1.5. Pregnancy Testing

Subjects who are WOCBP must have a negative serum pregnancy test result at Screening (Visit 1) to continue in the study, and a negative UPT at Baseline (Visit 2) prior to study entry. If the result of any post-treatment urine pregnancy test is positive, the subject will be withdrawn from the study and the subject’s pregnancy documented and followed. In addition, the investigator or designee will perform a urine pregnancy test for subjects who are WOCBP at Visit 6 (Post Treatment Safety Follow Up Visit).

13.1.6. Laboratory Assessments

All subjects are required to have a blood chemistry panel performed at Visit 1 (Screening) and at each protocol defined visit. A qualified staff member will collect non-fasting blood samples and ship the samples to a central laboratory for analysis. The following tests will be performed:

Chemistry Panel	Complete Blood Count
Albumin	Hematocrit
Alkaline phosphatase	Hemoglobin
Alanine aminotransferase (ALT)	Platelet count
Aspartate aminotransferase (AST)	Red blood cell morphology
Blood urea nitrogen (BUN)	Red blood cell count
Bicarbonate	White blood cell count
Calcium	White blood cell differential
Chloride	% & absolute
Creatinine	Basophils
Glucose	Eosinophils
Lactate dehydrogenase (LDH)	Lymphocytes
Phosphorus	Monocytes
Potassium	Neutrophils
Sodium	
Total bilirubin	
Total protein	

Uric Acid
Total cholesterol, LDL, HDL
Triglycerides

13.1.7. Virus Serology

All subjects will be required to have a QuantiFERON TB Gold, HIV, Hepatitis B and HCV serological blood test performed at screening. If the subject demonstrates to have serological evidence of any of these viruses, they will not be allowed to enroll to the study.

13.2. Adverse and Serious Adverse Events

13.2.1. Definition of Adverse Events

13.2.1.1. Adverse Event (AE)

An AE is the development of an undesirable medical condition or the deterioration of a pre-existing medical condition following or during exposure to a pharmaceutical product, whether or not considered casually related to the product. In clinical studies, an AE can include an undesirable medical condition occurring at any time, including baseline or washout periods, even if no study treatment has been administered.

The investigator should, when certain, report a diagnosis rather than the signs, symptoms or clinically significant abnormal laboratory values associated with the AE. Otherwise, signs, symptoms or abnormal laboratory values may be used to describe the AE.

Any CS abnormality discovered prior to the first study medication treatment should be reported as medical history, not as an AE.

All AEs that occur from the time of first study medication application (Visit 2) until 30 days after last study medication application must be documented in the subject's source documents and in Aclaris' EDC system.

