⁷ All subjects will be required to have virology testing for HepB (HBsAG), HCV(antibody), and HIV (antibody). If a subject demonstrates to have serological evidence HepB (HBsAG), HCV (antibody) or HIV (antibody), the subject will not be allowed to enroll to the study.

⁸ Canfield staff will review all photographs within 2 days of the photographs being submitted. If a re-take is required, Canfield will notify the site and the re-take photographs will need to be performed within 7 days of the visit. Prior to enrollment to the study, each subject's Visit 1 photos will be reviewed by a panel of board certified dermatologists to ensure that the subject's target areas for treatment meet the study entry criteria. In cases where the photographs do not properly characterize the disease (due to flashback and whitening on the photographs) the subjects will be allowed to enroll to the study based upon the Principal Investigator's clinical assessment of the subject.

⁹ At visit 2, following confirmation that the subject is approved for enrollment to the study, the site will weigh and dispense supplies of ATI-502 study medication and disposable droppers to the subject for at home application of the study medication.

¹⁰ All subjects will have their first application of study medication applied in the clinic during Visit 2. Subjects will continue to apply ATI-502 Topical Solution, 0.46% to all target areas twice a day for 4 weeks (Day 28) unless the subject meets the criteria for treatment interruption. If new areas of AD develop, subjects will be allowed to treat these areas with the ATI-502 study medication.

¹¹ Sites will be required to review with each subject the proper application of the study medication and remind that they must refrain from exercise that may cause excessive sweating, bathing or swimming for a period of 6 hours after the application of study medication. Subjects are also to be reminded that they may not apply moisturizers, emollients, or sunscreen to target AD areas during protocol treatment.

¹² All non-serious AEs will be collected from the time of first study medication application until the final study visit. Serious AEs will be collected from the time of consent through the final study visit.

¹³ A final safety follow up visit will be conducted at week 8 (Visit 6). For those subjects that discontinue the study early, they must return to the clinic 4 weeks following the last study medication application for a final safety visit.

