### **4.3 Safety Analyses**

The comprehensive safety analysis is based on all subjects in the Safety population.

The following sections detail the summaries performed on the safety data. Additional data handling rules including those for imputation of partially missing dates will be provided in a separate SAP document pertaining to data handling and programming specifications.

The baseline scores for vital signs, laboratory assessments and ECGs will be the last non-missing value collected on or before the date of the first application of study medication. This baseline will also be used for calculating change from baseline.

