#### **4.3.1 Adverse Events**

Adverse events will be coded using the MedDRA dictionary V21.1 and will be categorized by system organ class (SOC) and preferred term (PT). Only treatment emergent adverse events will be included in summary tabulation. All adverse events, including those that are not considered treatment emergent, will be included in the data listings.

To differentiate the study period in which an Adverse Event occurred, three categories will be defined based upon onset date. Adverse Events that had onset dates prior to the first application of study medication will be considered "prior". Adverse events with onset dates on or after the first application of study medication and within 30 days following the last application of study medication will be considered "on therapy" or equivalently "treatment emergent". Events with onset dates more than 30 days after the last application of study medication will be considered as "post-therapy".

Frequency tabulations will be presented by MedDRA SOC and preferred term, for all adverse events; study treatment-related, adverse events resulting in discontinuation of study treatment, serious adverse events and adverse events by maximum severity. Adverse events resulting in discontinuation will be those with 'action taken' recorded as 'drug withdrawn'.

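### A clinically significant Visit 2 laboratory abnormality can be tabulated as a treatment-emergent AE although the same value is the subject's baseline

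*Protocol*

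**What the plan says.** **Sorting of findings in the protocol.** Section 13.2.1.1 gives the general rule: "Any CS abnormality discovered prior to the first study medication treatment should be reported as medical history, not as an AE". Two sections add the other half of the rule, also by time of finding. For vital signs (13.1.2) a clinically significant abnormality is history if found earlier, "or as an AE if found after the first study medication application begins". For ECGs (13.1.4) it is history if found earlier, "or as an AE if found after the start of the first dose of study medication". Section 13.1.6 on laboratory tests has no rule of this kind.

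**Timing at Visit 2.** Table 2 schedules chemistry and CBC at every visit, including Visit 2 (Day 1). Footnote 10 says: "All subjects will have their first application of study medication applied in the clinic during Visit 2". On the laboratory route, section 13.1.6 says: "A qualified staff member will collect non-fasting blood samples and ship the samples to a central laboratory for analysis". Sections 12.4 and 12.5 require the Visit 2 SAD and SPA to be done before the first application. No equivalent instruction exists for Visit 2 bloods or vital signs.

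**Classification in the SAP.** Section 4.3 sets the safety baseline: "The baseline scores for vital signs, laboratory assessments and ECGs will be the last non-missing value collected on or before the date" of first application. Section 4.3.1 defines the treatment-emergent class as "Adverse events with onset dates on or after the first application of study medication", up to 30 days after the last one. AEs with an earlier onset are *prior*. Only treatment-emergent events are tabulated; the rest are listed.

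**The concern.** Three criteria decide where a finding goes: when it was discovered (protocol), when it began (SAP section 4.3.1), and the date on which the value was collected (SAP section 4.3, for baseline). They agree on every day except Day 1. On that day the baseline window and the treatment-emergent window overlap, and the laboratory result is likely to arrive after the drug has been applied.

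A single blood value can therefore appear as a subject's reference point in the laboratory summary, with change zero by construction, and as an event arising on drug in the AE table. Safety and tolerability are the primary outcome and there is no control arm, so no comparator rate would show that the event was there before treatment.

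**Working it through.** The plan states no figure on this point: the study is descriptive and the sample size of 30 has no formal basis. The check is a trace of the rules, followed by simple arithmetic for scale.

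**Trace for a Visit 2 blood sample drawn before dosing**

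1. The sample is taken on Day 1 (Protocol Table 2) and the drug is applied in clinic at the same visit (footnote 10).
2. The sample is shipped to a central laboratory (13.1.6). Results after dosing are the natural reading, although no turnaround is given. Nothing requires Visit 2 results before the application. Where the protocol wants a result first it says so: QuantiFERON before enrolment (Table 2, footnote 6), and investigator review of the "screening ECG prior to Visit 2" (13.1.4). Exclusion criterion 7 refers to Visit 1 laboratory values only.
3. A clinically significant abnormality learned of after dosing was not discovered before treatment, so the history rule in 13.2.1.1 does not capture it. The same section allows an AE to arise in a baseline period without treatment, so reporting it as an AE is open to the investigator.
4. Dated to its sample, the AE has onset on Day 1. SAP section 4.3.1 works from onset dates and gives no clock-time rule and no comparison with baseline, so the event can be counted as treatment-emergent.
5. SAP section 4.3 takes the same Day 1 value as baseline.

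**If the sample is drawn after dosing.** This is equally permitted. The AE classification may then be right, but the baseline is an on-treatment value, and changes at Visits 3 to 6 are measured from it. The same applies to Visit 2 vital signs taken after the application.

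**Other routes**

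| Source of finding | Known before dosing? | Outcome |
|---|---|---|
| Visit 1 labs and vital signs | Yes, in the normal course | History; not affected |
| Screening ECG | Yes, reviewed before Visit 2; no Visit 2 ECG is scheduled | History; not affected |
| Visit 2 vital signs read before dosing | Yes, read on the spot | History; not affected |
| Visit 2 vital signs read after dosing | No | AE under 13.1.2, and also the baseline value |
| Visit 2 labs | Normally not | Can be both AE and baseline |

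**Scale.** One subject in 30 is 1/30 = 3.3 percentage points. This is a ceiling for two reasons. A subject who already has another TEAE adds nothing to the any-TEAE rate. Replacement of non-completers (Protocol 7.7) can also raise the Safety Population above 30.

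The documents give no rate for such findings. If p is the assumed chance that a subject has a Visit 2 abnormality reported this way, the expected number is 30p and the chance of at least one is 1 − (1 − p)^30:

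| Assumed p | Expected subjects | Chance of at least one |
|---|---|---|
| 0.5% | 0.15 | 14% |
| 1% | 0.3 | 26% |
| 2% | 0.6 | 45% |
| 5% | 1.5 | 79% |
| 10% | 3.0 | 96% |

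These rows show sensitivity to p. None of them is an estimate.

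**The case against.** The strongest reply is that the protocol never says a laboratory abnormality found after dosing is an AE. That wording exists only for vital signs and ECGs. Section 13.2.1.1 defines an AE as a condition that develops or worsens during or after exposure, and asks for AEs occurring from first application. A value already abnormal in a pre-dose sample does not fit that definition. The SAP compares onset with the application itself, and SAP section 4.3 refers to a separate data-handling document that might hold a same-day rule. Several steps must all occur, and screening reduces the chance: neutrophils and platelets must be normal, Visit 1 abnormalities that make a subject a poor candidate are excluded, and screening lasts at most 14 days. Any error overcounts AEs, which is the cautious direction, and every AE is listed.

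Much of this stands. The outcome is possible rather than certain, and few subjects are likely to be involved. A reader might infer that pre-treatment abnormalities in general enter the AE tables, or that a vital-sign finding already recorded as history becomes an AE when seen again at Visit 3. The documents do not support either reading. Section 13.1.2 keeps a finding made before first application as history, the AE definition supplies a new-or-worse condition, and the SAP's *prior* class keeps earlier onsets out of the tables.

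The reply does not close the Day 1 gap. Section 13.2.1.1 also admits baseline-period events, so its definition does not settle the matter. The SAP's categories rest on onset dates, and a date alone cannot order two things on the same day. The only data-handling rule named for the separate document is imputation of partial dates. Listings would show the event but would not correct the table. Overcounting is not harmless when the laboratory tests concerned include those that Protocol section 9.3 and Table 4 single out for monitoring.

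**Conclusion.** The point holds for clinically significant Visit 2 laboratory abnormalities. They can be counted as treatment-emergent while the same value serves as baseline. Because the order of sampling and application is not fixed, the Visit 2 baseline for laboratory tests and vital signs can also be post-dose.

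The conclusion assumes that results return after the application, that the investigator reports the finding as an AE, that onset is dated to the sample, and that the separate data-handling document has no same-day rule. The number affected cannot be derived from the documents and is probably small; each subject adds up to 3.3 percentage points to a TEAE rate. The point is modest in size but worth correcting, because sorting by discovery is a stated rule, the AE tables carry the primary outcome, and the correction is cheap.

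**What to change.** 1. **Protocol Table 2, 13.1.2 and 13.1.6:** state that Visit 2 blood samples and vital signs are taken before the first application, as 12.4 and 12.5 already do for SAD and SPA.
2. **Protocol 13.2.1.1:** classify an abnormality by when the sample or measurement was taken relative to first application, whenever it was discovered. Report a pre-existing finding as an AE only if it worsens after first application.
3. **SAP 4.3.1:** for Day 1 onsets, use a before/after-first-application flag. Class a finding from a confirmed pre-dose baseline sample as *prior* unless it worsens. Keep Day 1 events of unknown timing as treatment-emergent.

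The restriction in item 3 to confirmed pre-dose samples matters. Classing every finding in a baseline sample as *prior* could hide a real Day 1 event, since the SAP baseline accepts any value from that date.

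The cost is a few sentences in each document and one extra field on the AE form. The TEAE count may fall slightly.
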